3.4.3 Cervical Length Determination

The length of the cervix will be measured according to the transvaginal ultrasound method described by Iams et al.¹⁵ With a real-time ultrasound probe placed in the anterior fornix of the vagina while the woman's bladder is empty, the appropriate sagittal view will be obtained by the location of the triangular area of echodensity at the external os, a V-shaped notch at the internal os, and a faint line of echodensity or echolucency between the two. After the initial image is obtained once the probe is in place, the probe will be withdrawn until the image blurs, and then the probe will be reapplied with only enough pressure to restore the image. The cervix will be measured three times along the line made by the interface of the mucosal surfaces, with calipers placed at the external and internal os. Dynamic change in cervical length will be considered by observing for spontaneous dynamic change or by applying mild fundal pressure for 15-30 seconds and then re-measuring the cervical length. The final cervical measurement reported will be the shortest best measure that clearly meets the above criteria – an averaging approach will not be used.

All cervical length measurements employed for screening and enrollment will be performed by a sonographer who has been trained and certified in the appropriate technique. Documentation of education and proficiency in appropriate technique and competency in cervical assessment will be required. Required documentation includes a Fetal Medicine Foundation Certificate of Competence in cervical assessment, or certification through the Perinatal Quality Foundation's Cervical Length Education and Review (CLEAR) program, or sonographer participation in a previous NICHD study.

An advisory committee of ultrasound experts will be assembled to review a random sampling of approximately 10-15% of enrollment vaginal ultrasound cervical length measurements as validation of appropriate imaging techniques.

3.4.4 Exclusion Criteria

1. Cervical dilation (internal os) 3 cm or greater on digital examination or evidence of prolapsed membranes beyond the external cervical os either at the time of the qualifying cervical ultrasound examination or at a cervical exam immediately before randomization.
2. Monoamniotic gestation, due to increased risk of adverse pregnancy outcome.
3. Twin-twin transfusion syndrome, due to increased risk of adverse pregnancy outcome.
4. Evidence of severe IUGR (<5th percentile for gestational age) in either fetus.

5. Fetal anomaly in either twin or imminent fetal demise. This includes lethal anomalies, or anomalies that may lead to early delivery or increased risk of neonatal death e.g., gastroschisis, spina bifida, serious karyotypic abnormalities. An ultrasound examination from 14 weeks 0 days to 23 weeks 6 days by project EDC must be performed prior to randomization to evaluate the fetuses for anomalies.
6. Placenta previa, because of risk of bleeding and high potential for indicated preterm birth.
7. Active vaginal bleeding greater than spotting at the time of randomization, because of potential exacerbation due to pessary placement.
8. Symptomatic, untreated vaginal or cervical infection, also because of potential exacerbation due to pessary placement. Patients may be treated and if subsequently asymptomatic, randomized.
9. Active, unhealed herpetic lesion on labia minora, vagina, or cervix due to the potential for significant patient discomfort or increasing genital tract viral spread. Once lesion(s) heal and the patient is asymptomatic, she may be randomized. History of herpes is not an exclusion.
10. Rupture of membranes due to likelihood of pregnancy loss and preterm delivery as well as the risk of ascending infection which could be increased with pessary placement.
11. More than six contractions per hour reported or documented prior to randomization. It is not necessary to place the patient on a tocodynamometer.
12. Known major Mullerian anomaly of the uterus (specifically bicornuate, unicornuate, or uterine septum not resected) due to increased risk of preterm delivery which is unlikely to be affected by progesterone.
13. Any fetal/maternal condition which would require invasive in-utero assessment or treatment, for example significant red cell antigen sensitization or neonatal alloimmune thrombocytopenia.
14. Major maternal medical illness associated with increased risk for adverse pregnancy outcome or indicated preterm birth (treated hypertension requiring more than one agent, treatment for diabetes prior to pregnancy, chronic renal insufficiency defined by creatinine >1.4 mg/dL, conditions treated with chronic oral glucocorticoid therapy, conditions requiring anti-coagulation therapy). Specifically, patients with seizure disorders, HIV, and other medical conditions not specifically associated with an increased risk of indicated preterm birth are **not** excluded. Prior cervical cone/LOOP/LEEP is not an exclusion criterion.
15. Planned cerclage or cerclage already in place since it would preclude placement of a pessary.
16. Planned indicated delivery prior to 35 weeks.
17. Planned or actual progesterone treatment of any type or form after 15 weeks 6 days during the current pregnancy.
18. Allergy to progesterone, silicone, or excipients in the study drug, including peanuts or peanut oil.
19. Known, suspected or history of breast cancer because breast cancer is a contraindication to the active study medication.
20. Known liver dysfunction or disease because liver disease is a contraindication to the active study medication.
21. Participation in another maternal/fetal interventional study that influences gestational age at delivery or neonatal morbidity or mortality.
22. Participation in this trial in a previous pregnancy. Patients who were screened in a previous pregnancy, but not randomized, do not have to be excluded.

23. Prenatal care or delivery planned elsewhere unless the study visits can be made as scheduled and complete outcome information can be obtained.

3.5 *Informed Consent Criteria*

Written informed consent must be obtained from patients before they can be screened for the study by cervical ultrasound unless the ultrasound is clinically indicated or part of routine clinical care. Patients who are eligible for the study because of the ultrasound results will be asked to sign another consent form to participate in the trial. Full disclosure of the nature and potential risks of participating in the trial is to be made.

Each center will develop its own consent forms according to the requirements of its own institutional review board using the model screening and study consent forms in Appendix B. Each center will also develop its own patient research authorization documents, as required by the HIPAA Privacy Rule, following the guidelines of its own institution. A copy of the signed screening consent form and, if applicable, the consent form for the study will be provided to the patient.

Women who are not fluent in English will be enrolled by a person fluent in their language, if possible. Both verbal and written informed consent and authorization will be obtained in that language; if this is not possible the patient will be excluded.

3.6 *Randomization Method and Masking*

Consenting women will initially be assigned to progesterone, pessary or placebo in a 1:1:1 ratio according to a randomization sequence prepared and maintained centrally by the Biostatistical Coordinating Center (BCC). The two study medication arms of the study (progesterone or placebo) are double masked; neither the patient nor the clinical staff will be aware of the treatment assignment.

The simple urn method will be used to generate the randomization sequences because it provides a high probability of balance in treatment assignments, it is unpredictable, and it allows an explicit randomization analysis to be conducted with relative ease.^{34,35} Randomization will be stratified by clinical site to assure balance between the two treatment groups with respect to anticipated differences in the clinic populations and possible differences in patient management.

4 Study Procedures

4.1 Screening for Eligibility and Consent

All women with twin gestation presenting for prenatal care before approximately 24 weeks gestational age are potentially eligible for screening. If a patient appears to meet the criteria for screening, she will be told about the study and asked to sign an informed consent form for screening (see Appendix B.1 for the model screening consent form) unless she has already been identified as having cervical length less than 30 mm from a transvaginal ultrasound conducted by a study certified sonographer as part of clinical care. Cervical length is assessed with a transvaginal ultrasound conducted in a standardized fashion described in Section 3.4.3. All measurements will be conducted by a sonographer who has been previously certified for this or one of the previous studies. If the patient has a cervical length of 30 mm or more, but less than 35 mm she may be rescreened once within a one to four week window, if the patient is still less than 24 weeks gestation.

Patients who have had either a transabdominal or transvaginal ultrasound that has a documented short cervical length by non-study certified personnel are eligible for inclusion in the study but would still have to grant informed consent for cervical length screening followed by an official study ultrasound.

Inclusion/exclusion criteria will be reviewed with the patient's chart. Eligible patients will be asked for written informed consent to participate in the trial (see Appendix B.2 for the model consent to study form). If an obstetrical ultrasound examination to evaluate the fetuses for anomalies has not been performed at 14 weeks of gestation or later, one must be performed before randomization. The results of this ultrasound must be reviewed to check for exclusion criteria, and if it is the patient's first ultrasound with dating parameters, gestational age. The results of the dating and/or anatomy ultrasounds may be made available to the patient's physician.

Immediately prior to randomization each patient will also undergo a speculum examination (followed by a digital exam if necessary) to rule out cervical dilation and cervical infection. A cervicovaginal fluid sample, vaginal Gram stain, and vaginal pH will be collected to assess for local inflammation, vaginitis, and fetal fibronectin (quantitative).

4.2 Randomization

Eligible and consenting patients will be randomized by certified research staff using an internet-based randomization system maintained by the BCC. The patient will be assigned either to pessary or to a study drug code number corresponding to a blinded study medication kit.

4.3 Baseline Procedures

In addition to information collected for eligibility, project gestational age, and project EDC determination, the following information will be obtained at randomization from a patient interview followed by a review of her chart:

- Demographic information: age, race, insurance status
- Medical history: pre-pregnancy weight, current weight, height, chronic disease history
- Obstetrical history including outcome of all prior pregnancies and history of vaginal bleeding in the current pregnancy
- Social history: marital status, years of education, alcohol use, tobacco use and other maternal drug use

- Current pregnancy complications including sexually transmitted infections and vaginal infections.

Women randomized to pessary will be evaluated by an obstetric care provider (nurse practitioner, nurse midwife, or physician) who has been trained in the proper technique of pessary sizing and placement. The provider will fit the patient for and place an Arabin pessary according to standard technique so that it encircles the cervix and rests in the anterior and posterior fornices.

Women randomized to vaginal progesterone or placebo will place the first dose of study product under supervision in the clinic. The patient will receive instruction on daily use of the study product and will receive a month's supply of study product.

4.4 Study Procedures

All patients will receive a phone call from a research nurse to assess compliance and symptoms within one week of randomization. If a patient in the pessary group is experiencing discomfort she will be asked to come in to assess the pessary for fit and possible replacement with a different size.

All patients will have monthly assessments (in-person or virtual) with a research nurse/provider for compliance, symptoms related to treatment, review of recent hospitalization(s), and any additional treatment received for preterm labor, such as corticosteroids or tocolytics since their last visit. Patients who are receiving vaginal progesterone or placebo will receive a monthly supply of study drug and compliance will be assessed monthly by a capsule count.

A second set of cervicovaginal fluid samples will be collected if an in-person study visit occurs between 24 to 32 weeks by project gestational age. The second samples will include a cervicovaginal fluid sample, vaginal Gram stain and vaginal pH (without a speculum exam) to assess for local inflammation, vaginitis, and fetal fibronectin (quantitative). The samples will be evaluated not only for their potential individual association with outcomes, but also to examine any potential interval changes that may be associated with the assigned treatment arm. Women randomized to pessary will have at least one in-person visit to undergo a digital examination to ensure appropriate pessary placement.

At the second study visit after randomization, patients will be asked to complete a questionnaire summarizing their experience with the pessary (if randomized to pessary) or study medication (if randomized to the study medication group). The questionnaire will be administered again at 36 weeks gestation.

Therapy will be continued until 34 weeks, 6 days to 36 weeks, 0 days of gestation, at which time all patients should have a final study visit scheduled. Women in the pessary arm will have the device removed.

4.5 Patient Management and Follow-up

If a patient experiences rupture of the membranes, the study treatment should be stopped.

The pessary may be removed as necessary to evaluate vaginal bleeding contractions, preterm labor, or other conditions. The pessary will be reinserted if symptoms resolve and the cervix is less than 3 cm dilated. A patient will be instructed to call if the pessary comes out (fully or partially), becomes dislodged or if she removes it herself so that arrangements for a replacement pessary can be made. If the patient is uncomfortable, a replacement pessary may be inserted.

Indications for pessary removal are as follows:

1. Painful, regular uterine contractions occurring at least every 10 minutes in order to facilitate accurate assessment of cervical dilation and effacement, especially if cervical examination with the pessary in place suggests dilation or progressive cervical shortening.
2. Confirmed rupture of membranes — the initial assessment for rupture can be performed with the pessary in place, but once confirmed, the pessary should be removed.
3. Confirmed diagnosis of clinical chorioamnionitis.
4. Vaginal bleeding greater than menses — if the bleeding ceases and there are no other contraindications, the pessary can be replaced.
5. Development of significant cervical edema with a cervical herpetic lesion.
6. Cervical laceration or significant edema.
7. At the patient's request because of significant discomfort or other reasons.

If a patient presents with symptoms of vaginitis, she should be treated as per local clinical standards. If the patient has a pessary, it should be left in place; if she is in one of the study medication arms, she should be instructed to continue her daily use of study medication while she is being treated.

No attempt will be made to alter or mandate clinical management of the subjects. Sexual intercourse is not expressly prohibited in this study. However, the use of serial cervical length ultrasounds, prophylactic tocolytic drugs or cerclage is discouraged. If a patient is hospitalized, the patient should be told to continue her study medication and additional supplies made available if necessary. Otherwise patients admitted to hospital for preterm labor should be managed according to institutional policy.

Infants will be followed to discharge or until 28 days after the expected date of delivery as determined by project gestational age, whichever is longest. Maternal and neonatal records will be reviewed and a follow-up telephone interview conducted to capture neonatal and maternal outcomes.

4.6 Adverse Event Reporting

Detailed information concerning adverse events will be collected and evaluated throughout the conduct of the protocol.

The NICHD Program Scientist and the BCC will be notified within seventy-two hours of any maternal death, neonatal death, or life threatening maternal event by email/phone/fax, if the event occurred in a MFMU Network hospital. For any maternal death, neonatal death, or life threatening maternal event occurring outside a MFMU Network hospital, the adverse event must be reported to the NICHD and the BCC within twenty-four hours of being notified. These and other adverse events deemed serious, unexpected and definitely, possibly or probably related, will be immediately (within twenty-four hours of notification) forwarded by the BCC to the DSMC Chair, NIH representative, and any other DSMC member who requests notification. If a death is reported, a copy of the patient's medical record will be made.

Adverse events which do not qualify under the above definition must be reported to the BCC within 7 days of being notified. These adverse events will be collected and sent to the DSMC Chair, NIH representative, and any other requesting DSMC member on a monthly basis. The DSMC Chair decides whether the adverse event reports should be disseminated to the rest of the committee, whether a follow-up call or meeting is required, and whether the treatment assignment should be unmasked. NICHD representatives may also request follow-up of specific events. All adverse events will be considered along with other interim safety data in the DSMC deliberations.

An FDA Investigational Device Exemption safety report will be completed for any suspected adverse reaction to the pessary that is both serious and unexpected. Likewise an FDA Investigational New Drug

safety report will be completed for any suspected adverse reaction to the study medication, whether active or placebo.

The only indication for breaking the randomization code is when it is medically necessary to unmask the study drug assignment to be able to treat the patient.

4.7 Study Outcome Measures and Ascertainment

4.7.1 Primary Outcome

The primary outcome is delivery or fetal demise of either twin prior to 35 weeks 0 days (as determined by the project gestational age).

4.7.2 Maternal Secondary Outcomes

- Randomization to delivery (or fetal demise) interval
- Gestational age at delivery
- Preterm delivery or fetal demise of either twin prior to 28 weeks, 32 weeks, and 37 weeks
- Delivery of at least one liveborn infant at ≥ 32 weeks, ≥ 35 weeks, and ≥ 37 weeks
- Preterm premature rupture of membranes (pPROM)
- Spontaneous preterm delivery (following preterm labor or pPROM) < 35 weeks and < 32 weeks
- Indicated preterm delivery < 35 weeks
- Cesarean delivery
- Chorioamnionitis
- Maternal antepartum hospitalization days
- Maternal antibiotic or antifungal use for vaginal infection
- Vaginal infection as assessed by local clinical diagnosis
- Side effects including symptomatic vaginal discharge or discomfort
- Discontinuation of treatment and reason

4.7.3 Fetal and Neonatal Secondary Outcomes

- Fetal or neonatal death
- Twin-twin transfusion syndrome
- Duration of ventilator support
- Duration of supplemental oxygen
- Seizures requiring treatment
- Small for gestational age defined as $< 5^{\text{th}}$ percentile weight for gestational age, assessed specifically by sex and race of the infant based on United States birth certificate data
- Intraventricular hemorrhage (IVH) grades III or IV as determined by cranial ultrasounds performed as part of routine clinical care and classified based on the Papile classification system

- Retinopathy of prematurity (ROP). This diagnosis will be reached when an ophthalmologic examination of the retina has been performed and ROP is diagnosed at Stage I (demarcation line in the retina) or greater.
- Respiratory distress syndrome (RDS) defined as the presence of clinical signs of respiratory distress (tachypnea, retractions, flaring, grunting, or cyanosis), with an oxygen requirement and a chest x-ray that shows hypoaeration and reticulogranular infiltrates.
- Bronchopulmonary dysplasia (BPD) defined as oxygen requirement at 28 days of life or at 36 weeks project gestational age for infants born before 32 weeks.
- Necrotizing Enterocolitis (NEC), defined as modified Bell Stage 2 or 3 where stage 2 represents clinical signs and symptoms with pneumatosis intestinalis on radiographs and stage 3 is defined as advanced clinical signs and symptoms, pneumatosis, impending or proven intestinal perforation.
- Hyperbilirubinemia. Peak total bilirubin of at least 15 mg% or the use of phototherapy
- Neonatal infectious morbidity
 - Sepsis (within 72 hours and > 72 hours after birth). The diagnosis of sepsis will require the presence of a clinically ill infant in whom systemic infection is suspected with a positive blood, CSF, or catheterized/suprapubic urine culture; or, in the absence of positive cultures, clinical evidence of cardiovascular collapse or an unequivocal radiograph confirming infection.
 - Suspected sepsis. The diagnosis of suspected sepsis will include infants with suspicious clinical findings of infection, but no positive cultures or radiographs.
 - Pneumonia. The diagnosis of pneumonia will be confirmed by radiograph or positive blood culture.
- Composite neonatal outcome comprised of fetal or neonatal death or RDS, Grade 3 or 4 IVH, PVL, Stage 2 or 3 NEC, BPD, Stage III or higher ROP, or early onset sepsis. Occurrence of any of the individual components is considered indicative of the outcome
- Length of hospital stay, need for NICU or intermediate care admission and length of stay if admitted

5 Statistical Considerations

5.1 Data Relevant to the Primary Outcome

For this trial as in the MFMU Network STTARS trial, the primary outcome is fetal death or preterm delivery before 35 weeks for either twin. In the STTARS trial the primary outcome rate in all twins (regardless of cervical length) was approximately 40% with no difference seen by treatment group. In the current trial, a higher incidence of the primary outcome is expected in the placebo group since these women will have a shorter cervical length.

This is confirmed by the data from the Network presented in Section 2.2.2. In the Preterm Prediction Twin Cohort, cervical length less than 30 mm at 22-24 weeks was associated with a 56% rate of preterm delivery or fetal loss < 35 weeks. In the STTARS study, there were very few (10) patients with cervical length less than 30 mm at 14-20 weeks, of which 5 (50%) had a preterm delivery or fetal loss before 35 weeks (the primary outcome for STTARS). However, 56% (10/18) of those with cervical length < 32 mm (10th percentile) had the same outcome. Therefore, it is reasonable to assume that the primary outcome rate in the placebo group would be between 50 and 60%.

5.2 Sample Size and Power

A one-third reduction in preterm birth < 35 weeks was selected as being clinically meaningful. It is assumed that pessary and micronized progesterone are more likely to be effective for preventing spontaneous rather than indicated preterm birth. If 20% of the preterm births at this gestation are indicated (lower than that typically expected since these women will all have a short cervix) and if there is a 40% reduction in spontaneous preterm birth and no reduction in indicated preterm birth, then the overall effect size would be slightly less than a one-third reduction in all preterm births.

Table 3 below shows the sample sizes required to detect 30-33% reduction in PTB < 35 weeks if the rate in the placebo group is 50-60%, with type I error 2.5% 2-sided and power of 90%. Type I error was chosen to be 2.5% 2-sided since there will be two primary comparisons (between pessary and placebo and between progesterone and placebo).

Table 3. Sample Sizes per Group for Different Primary Outcome Rates, Power and Effect Sizes²

Reduction in Primary Outcome Rate	% Power	Primary Outcome Rate in Placebo Group		
		50%	55%	60%
30%	80	210	180	150
	85	240	200	170
	90	270	230	190
33.3%	80	170	140	120
	85	190	160	140
	90	220	190	160

²Rounding up to next 10

In STTARS, women were given a test injection of progesterone (17- α hydroxyprogesterone caproate) and asked to return for randomization in three days or more. A total of 2.7% of women did not return or withdrew consent. Since a compliance run-in such as this is not feasible for PROSPECT, it is assumed conservatively that as many as 5% of the women drop out and effectively become crossovers. This would require an adjustment in the sample size of approximately 10.8%. Thus, adjusting for 5% crossover, a sample size of 630 patients is sufficient to detect a one-third reduction in the primary outcome rate of 55% in the placebo group with 90% power for either the pessary or the progesterone arm, and at least 80% power if the effect size is as low as 30%.

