5.4 Interim Analysis

The DSMC meets in person at least once per year and more often if recommended by the committee. Before each of the annual meetings, a formal detailed report will be written by the Biostatistical Coordinating Center (BCC) which presents all baseline variables, protocol adherence, side effects, all adverse events reported, as well as center performance in terms of recruitment, data quality, loss to follow-up and protocol violations.

Once sufficient patients have been accrued into the trial, the report will also include a formal interim analysis evaluating the primary outcome by treatment group. For this evaluation, a cohort of patients is chosen consisting of all patients randomized before a certain date so that the analysis cohort does not depend on gestational age at delivery.

The main statistical issue relevant to interim analysis is the problem of performing multiple tests of significance on accumulating data. For this trial, the group sequential method of Lan and DeMets will be used to characterize the rate at which the type I error is spent.³⁶ This method is flexible with regard to the timing of the interim analyses. Asymmetric stopping boundaries will be used for the Lan-DeMets procedure. The upper boundary which describes the stopping rule for benefit will be based on 1-sided type I error of .0125 and the Lan-DeMets generalization of the O'Brien-Fleming boundary. The lower boundary will be based on a less stringent stopping rule: 1-sided type I error of .05 and the Lan-DeMets generalization of the Pocock type boundary. If recruitment proceeds as planned and annual analyses are conducted, it is expected that two interim analyses will be conducted at approximately 35% and 65% of the final sample size of 630.

If a maternal death occurs after randomization and before discharge following delivery recruitment to the trial will be paused until the DSMC has been convened to determine whether the study should proceed.

It is often useful to calculate conditional power given the observed data to date, and conditional on the future data showing the originally assumed design effect. If this conditional power is low (under 10 percent) the DSMC may consider termination for futility if the accrual rate is slow with confidence that the Type II error is not greatly inflated.³⁷

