Assumptions:	❖ Outcome event=delivery < 35 ⁰ weeks gestation or fetal loss ❖ Placebo group event rate =55% ❖ Progesterone group event rate =36.7% (33% reduction) ❖ Pessary group event rate=36.7% (33% reduction) ❖ Type I error = 2.5% (two sided with two primary comparisons) ❖ Power =90% ❖ Adjustment for 5% crossover	Secondary:	❖ Randomization to delivery interval ❖ Gestational age at delivery ❖ Neonatal morbidity and mortality ❖ Lower genital tract or urinary tract infection ❖ Physician interventions including bedrest, cerclage, labor inhibition therapy
Interim Analysis:	❖ Lan-DeMets group sequential method	TIMETABLE	
		Enrollment	❖ April 2015 to September 2018
		Data Collection	❖ April 2015 to June 2019
		Closeout/Analysis	❖ June 2019 to May 2020

References

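### Cheap improvement, not an error: a Holm step-down rule would keep the 5% familywise error of the fixed 2.5% split and could add a second positive conclusion when both treatments work

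*Combined protocol and SAP*

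**What the plan says.** Section 5.2 sets the level for each primary comparison: "Type I error was chosen to be 2.5% 2-sided since there will be two primary comparisons", the two being "between pessary and placebo and between progesterone and placebo". Appendix A repeats it: "Type I error = 2.5% (two sided with two primary comparisons". Section 5.4 carries the same split into monitoring: "The upper boundary which describes the stopping rule for benefit will be based on 1-sided type I error of .0125", with O'Brien-Fleming-type Lan-DeMets spending and looks expected at about 35% and 65% of 630. The lower boundary is separate and less strict (Pocock type, one-sided .05).

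Appendix A plans on the same effect in both active arms: "Placebo group event rate =55"%, "Progesterone group event rate =36.7% (33% reduction") and "Pessary group event rate=36.7% (33% reduction"). Section 5.2 states power per comparison: "with 90% power for either the pessary or the progesterone arm". It sets no target for succeeding on both.

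Section 5.5 describes the primary analysis as a comparison of two proportions, with relative risks and confidence intervals. It names no step-down or alpha-recycling rule and no confidence level. Section 5.4 does not say what happens to the remaining comparison once one has crossed its upper boundary.

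**The concern.** Under the fixed split, each comparison faces the 2.5% two-sided level whatever the other one shows. Once one null hypothesis has been rejected, only one is left that could still be falsely rejected, so the second can be tested at the full 5% without exceeding the familywise limit. The fixed split leaves that margin unused, and it does so in the scenario of Appendix A, where both treatments work.

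At stake is the second of two primary hypotheses (Section 1.2). If pessary were significant at 2.5% and progesterone had p = 0.03, the planned test would not reject for progesterone. A test with the same familywise error would.

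**Working it through.** **Inputs.** Placebo rate 55%; one-third reduction (36.7%) in each active arm, or 30% as the smaller effect; 2.5% two-sided per comparison; 1:1:1 allocation of 630, so 210 per arm; 5% crossover (Sections 3.6 and 5.2, Appendix A). Section 5.1 puts the placebo rate between 50% and 60%, so 50% serves as the lower case.

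**Step 1: the plan's own figure.** Per-group size for two proportions, pooled variance under the null, no continuity correction:

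n = [z(α/2)·√(2p̄(1−p̄)) + z(β)·√(p0(1−p0) + p1(1−p1))]² / (p0−p1)²

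With p0 = 0.55, p1 = 0.3667, α = 0.025 two-sided (z = 2.241) and 90% power, n = 182, which Table 3's rounding takes to 190. Crossover: 190/0.95² = 210.5, about 210 per arm, and 3 × 210 = 630. All 18 cells of Table 3 reproduce in this way.

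Crossover is modelled as a 5% dilution of the risk difference. The active rate becomes 0.55 − 0.95 × 0.55/3 = 0.376 (one-third reduction) or 0.55 − 0.95 × 0.55 × 0.30 = 0.393 (30% reduction). The formula then gives 91.3% and 83.9% power with 210 per arm, against the stated 90% and at least 80%. The plan meets its own target.

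**Step 2: fixed-sample comparison.** One million simulated three-arm trials per scenario, 210 per arm, one shared placebo arm, pooled z tests. Bonferroni uses a critical value of 2.241 for both comparisons. Holm uses 2.241 for the first rejection and 1.96 for the other. Both treatments effective:

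| Placebo rate, reduction | Per comparison: Bonferroni → Holm | Both: Bonferroni → Holm |
|---|---|---|
| 55%, one-third | 91.8% → 94.0% | 86.2% → 90.6% |
| 55%, 30% | 84.9% → 88.0% | 75.7% → 81.9% |
| 50%, one-third | 85.9% → 89.7% | 77.2% → 84.8% |

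(The simulated 91.8% differs from the formula's 91.3% because binomial counts are discrete.)

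**Step 3: where there is no gain.** Holm makes its first rejection exactly when Bonferroni does. The chance of at least one success is therefore identical: 97.5% (55%, one-third) and 94.1% (55%, 30%). If one arm has a one-third reduction and the other none, power for the effective arm moves by at most 0.2 points (91.9% to 92.1%). The size needed for a single effective arm stays at 182 per group before adjustment, so 630 does not fall.

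**Step 4: error rates.** With no effect in either arm, the familywise error is the same for both procedures, about 5% two-sided. If one arm works and the other does not, the ineffective arm's nominal one-sided false-positive rate goes from 1.25% to at most 2.5% (simulated with binomial counts: about 1.4% to 2.5%).

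**Step 5: with monitoring.** Normal simulation, correlation 0.5 from the shared placebo arm, looks at 35%, 65% and 100%, with the remaining comparison carried on to the planned end. Upper boundaries (z) are 4.06, 2.89 and 2.26 at one-sided .0125, and 3.61, 2.55 and 1.99 at .025. At a 55% placebo rate with a one-third reduction, power per comparison goes from 91.7% to 94.3% and for both from 85.8% to 91.1%. With a 30% reduction the figures are 84.2% to 88.2% and 74.7% to 82.6%. The one-sided familywise error with no effect in either arm is 2.33% under both procedures.

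**The case against.** The strongest reply is that nothing is broken. The equal split controls the familywise error, agrees across Sections 5.2 and 5.4 and Appendix A, and meets the stated power, which is per comparison. The largest gains are for succeeding on both, which the plan never set as a target. Pessary and progesterone are also separate interventions with separate hypotheses, so a sponsor may reasonably want the same fixed standard of evidence for each. All of this stands, and it is why the point is an optional improvement.

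Four stronger readings are tempting, and the documents do not support them:

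- A reader might infer that the trial is underpowered or the sample size wrong. The 630 reproduces, and the power exceeds what is claimed.
- A reader might infer that Holm is free. It is not: the ineffective arm's false-positive rate can double when the other arm works, a second boundary set is needed, and the second comparison's interval no longer matches its test.
- A reader might infer that Holm raises power generally or allows a smaller trial. Step 3 shows otherwise.
- A reader might infer that a treatment with p between 0.025 and 0.05 would be declared ineffective. No section says so. It would only fail to reach significance, and its relative risk and interval would still be reported.

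A further objection concerns how the rule is written. If two-sided p-values are simply ordered, significant harm in one arm would relax the benefit test for the other, which does not fit the asymmetric boundaries of Section 5.4. That is correct, and the rule below is confined to benefit for this reason.

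**Conclusion.** The point holds as a cheap improvement. When both treatments work, a step-down rule adds about 2 to 4 percentage points of power per comparison and about 4 to 8 points for succeeding on both, at the same familywise error and with the same 630 women. It adds nothing to the chance of a first success and essentially nothing when only one treatment works.

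The size rests on these assumptions: equal effects in both active arms as in Appendix A, crossover acting as a 5% dilution of the risk difference (consistent with the plan's 10.8% inflation), and an overall limit of 5% two-sided, which is inferred from two comparisons at 2.5%. The gain under monitoring also requires the second boundary to be fixed in advance and the remaining comparison to continue.

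**What to change.** **Sections 5.2 and 5.5.** Keep 630 and the 2.5% planning level. Before any unblinded comparison, state that once one comparison is rejected for benefit at its 2.5% two-sided (.0125 one-sided) level, the other is tested for benefit at 5% two-sided (.025 one-sided). State that rejection for harm releases no alpha.

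**Section 5.4.** Specify a second O'Brien-Fleming-type Lan-DeMets upper boundary at one-sided .025 for the remaining comparison. It applies only after the other comparison has crossed its .0125 upper boundary, and only to the extent that the remaining comparison continues. Leave the lower boundary as it is.

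**Reporting.** Give 97.5% intervals for both comparisons, with a note that the interval for the comparison tested second may not match its test. State the change in the ineffective arm's false-positive rate (from about 1.25% to at most 2.5% one-sided).

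**Cost.** A short paragraph in the analysis plan and a second set of boundary values. No more patients and no change in conduct. If the sponsor prefers the fixed split, one sentence giving the reason is enough.
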